10.62 All other AEs

Submit via appropriate MCCC Case Report Forms (i.e., paper or electronic, as applicable) the following AEs experienced by a patient and not specified in Section 10.6:

10.621 Grade 2 AEs deemed *possibly, probably, or definitely* related to the study treatment or procedure.

10.622 Grade 3 and 4 AEs regardless of attribution to the study treatment or procedure.

10.623 Grade 5 AEs (Deaths)

10.6231 Any death within 30 days of the patient’s last study treatment or procedure regardless of attribution to the study treatment or procedure.

10.6232 Any death more than 30 days after the patient’s last study treatment or procedure that is felt to be at least possibly

treatment related must also be submitted as a Grade 5 AE, with a CTCAE type and attribution assigned.

11.0 Treatment Evaluation/Measurement of Effect

The International Myeloma Working Group (IMWG) uniform response criteria(23) will be used to assess response to therapy.

11.1 Terms and definitions

- **M-protein:** synonyms include M-spike, monoclonal protein and myeloma protein, paraprotein, M-component.

Serum M-protein level is quantitated using densitometry on SPEP except in cases where the SPEP is felt to be unreliable.

- M-proteins migrating in the β -region (usually IgA M-proteins)
- Cases in which the M-protein is so large and narrow on agarose (some specimens >4 g/dL) that they underestimate the actual immunoglobulin level (by greater than 1500 mg/dL) due to technical staining properties of the agarose gel.
- Cases in which there are multiple peaks of same M-protein (aggregates or dimers)

If SPEP is not available or felt to be unreliable (above examples) for routine M-protein quantitation, then quantitative immunoglobulin levels derived from nephelometry or turbidometry can be accepted, with the exception that quantitative IgG may not be used. However, this must be explicitly reported at baseline, and only nephelometry can be used for that patient to assess response. SPEP derived M-protein values and quantitative nephelometric immunoglobulin values cannot be used interchangeably.

Urine M-protein measurement is estimated using 24-h UPEP only. Random or 24 h urine tests measuring kappa and lambda light chain levels are not reliable and are not recommended.

FLC estimation is currently carried out using the serum FLC assay (Freelite, The Binding Site Limited, UK). Patients with kappa/lambda FLC ratio <0.26 are defined as having monoclonal lambda FLC and those with ratios >1.65 as having a monoclonal kappa FLC. The monoclonal light chain isotype is considered the involved FLC isotype, and the opposite light chain type as the unininvolved FLC type.

- **Response terms:** The following response terms will be used: stringent Complete Response (sCR), complete response (CR), very good partial response (VGPR), partial response (PR), Minimal Response (MR), stable disease (SD), and progressive disease (PD).

In addition, for each response category, there will be an “unconfirmed” response category, which will be for internal use, for the purpose of guiding decision making and test ordering. These designations will be applied at the time of the first measurement at which the quantitative aspect of the response category has been satisfied without the confirmation step having been satisfied. The designation “u” will precede the standard abbreviations, and will include usCR, uCR, uVGPR, uPR, uMR, uPD.

- **Measurable disease:** Patients who have a measurable serum or urine M-protein.

- Serum M-protein ≥ 0.5 g/dl

NOTE: Quantitative IgG may not be used for defining measurable disease

- Urine M-protein ≥ 200 mg/24 h
- Serum FLC assay: Involved FLC level ≥ 10 mg/dl provided serum FLC ratio is abnormal
- Bone marrow plasma cells $\geq 30\%$
- Measurable bone or extramedullary disease on imaging.

Measurable disease			
Cohort A (Smoldering MM),	Cohort B (Newly Diagnosed MM)	Cohort C (Relapsed/Refractory MM)	Cohort D (Relapsed on Len maintenance)

Patients who have a measurable serum or urine M-protein.
 
 ○ Serum M-protein ≥ 0.5 g/dl NOTE: Quantitative IgG may not be used for defining measurable disease ○ Urine M-protein ≥ 200 mg/24 h ○ Serum FLC assay: Involved FLC level ≥ 10 mg/dl provided serum FLC ratio is abnormal ○ Bone marrow plasma cells 	
Patients who have a measurable serum or urine M-protein.
 
 ○ Serum M-protein ≥ 0.5 g/dl NOTE: Quantitative IgG may not be used for defining measurable disease ○ Urine M-protein ≥ 200 mg/24 h ○ Serum FLC assay: Involved FLC level ≥ 10 mg/dl provided serum FLC ratio is abnormal ○ Bone marrow plasma cells 	
Patients who have a measurable serum or urine M-protein.
 
 ○ Serum M-protein ≥ 0.5 g/dl NOTE: Quantitative IgG may not be used for defining measurable disease ○ Urine M-protein ≥ 200 mg/24 h ○ Serum FLC assay: Involved FLC level ≥ 10 mg/dl provided serum FLC ratio is abnormal ○ Bone marrow plasma cells 	
Patients who have a measurable serum or urine M-protein.
 
 ○ Serum M-protein ≥ 0.5 g/dl NOTE: Quantitative IgG may not be used for defining measurable disease ○ Urine M-protein ≥ 200 mg/24 h ○ Serum FLC assay: Involved FLC level ≥ 10 mg/dl provided serum FLC ratio is abnormal ○ Bone marrow plasma cells

$\geq 30\%$ o Measurable bone or extramedullary disease on imaging.			
---	---	---	---

The serum free light chain (FLC) assay is of particular use in monitoring response to therapy in patients who have oligo-secretory or non-secretory disease and **should be used in assessing response only if the baseline serum and/or urine M proteins are not “measurable” as above, and the baseline level of the involved FLC is “measurable.”** When using this assay, it is important to note that the FLC levels vary considerably with changes in renal function and in patients with renal insufficiency, the levels of both the kappa and lambda may remain elevated, but the ratio normalizes with achievement of CR. Thus, both the level of the involved and the uninvolved FLC isotype (i.e., the involved/uninvolved ratio or involved-uninvolved difference) should be considered in assessing response. ***Patients included on the study on the basis of FLC alone (i.e., no measurable serum/urine M-protein) should be the only ones who are evaluated using FLC response criteria. The others should follow usual criteria and ignore FLC results*** with the exception of defining stringent complete response.

- **Evaluable disease:** Patients who do not have a “measurable” serum M-protein, serum free light chain, or urine M-protein.
- **Oligosecretory myeloma:** Patient with multiple myeloma who has NEVER had “measurable” serum M-protein or urine M-protein, but has had a detectable M-protein in his/her serum and/or urine and/or measurable serum free light chain.
- **Non-secretory myeloma:** Patient with multiple myeloma who has NEVER had a detectable M-protein in his/her serum and/or urine.

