3.13 Measurable disease as defined in section 11.0

3.14 Provide written informed consent.

3.15 Patient must be considered for treatment with an IMiD containing regimen.

3.16 ECOG Performance Status (PS) 0, 1, 2 or 3 (Appendix I).

3.17 The following laboratory values obtained \leq 14 days prior to registration:

- Hemoglobin \geq 7.0 g/dL
- Absolute neutrophil count (ANC) \geq 1000/mm³
- Platelet count \geq 50,000/mm³

- Total bilirubin $\leq 1.5 \times$ upper limit of normal (ULN) unless due to Gilbert's syndrome, in which case the direct bilirubin must be $\leq 1.5 \times$ ULN.
- Alanine aminotransferase (ALT) and aspartate transaminase (AST) $\leq 3 \times$ ULN ($\leq 5 \times$ ULN for patients with liver involvement)
- PT/INR/aPTT $\leq 1.5 \times$ ULN OR if patient is receiving anticoagulant therapy and INR or aPTT is within target range of therapy
- Calculated creatinine clearance ≥ 45 ml/min using the Cockcroft-Gault formula below:

Cockcroft-Gault Equation:

$$\text{Creatinine clearance for males} = \frac{(140 - \text{age})(\text{weight in kg})}{(72)(\text{serum creatinine in mg/dL})}$$

$$\text{Creatinine clearance for females} = \frac{(140 - \text{age})(\text{weight in kg})(0.85)}{(72)(\text{serum creatinine in mg/dL})}$$

3.18 Negative pregnancy test done ≤ 7 days prior to registration, for persons of childbearing potential only.
NOTE: If the urine test is positive or cannot be confirmed as negative, a serum pregnancy test will be required.

3.19a Willing to return to enrolling institution for follow-up (during the Active Monitoring Phase of the study).

3.19b Willingness to provide mandatory blood and bone marrow specimens for correlative research (see Section 14.0).

3.19c Willing to follow the requirements of the Pomalyst® REMS program

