4.0 Test Schedule

Tests and procedures	Active Monitoring Phase					
	Prior to registration		Prior to Day 1 Cycle 1	Prior to Day 1 Cycle 2	Prior to Day 1 Cycles 3-6	End of Treatment
	≤28 days	≤14 days				
Window				±3 days	±3 days	±7 days
Complete Medical History		X				
Physical exam, Wt, PS		X	X ³	X	X	X
Adverse event assessment		X		X	X	X
Pregnancy test ¹		X				
Height		X				
Hematology group: CBC with 5-part differential		X	X ³	X	X	X
Chemistry group to include serum creatinine, calcium, T.Bili, D. bili, AST, and ALT		X	X ³	X	X	X
LDH, Beta-2-microglobulin, Plasma cell assessment		X	X ³			
PT/PTT/INR		X				
TSH		X				
Electrophoresis of serum and urine		X	X ^{3,5}	X ⁵	X ⁵	X ⁵
Immunofixation or mass fixation of serum and urine		X		X ⁷	X ⁷	X ⁷
Affected Serum Immunoglobulin ²		X	X ³	X	X	X
Serum Immunoglobulin free light chain		X	X ³	X	X	X
WBLDCT ³ or PET/CT	X			X ³	X ³	
Bone marrow aspirate and biopsy	X					
Patient Medication Diary (Appendix II)			X	X	X	
Research bone marrow sample ^R	X			X ⁶		X ⁴
Research blood sample ^R	X			X ⁶		X ⁴

Cycle 1 = 21

Cycles 2-6 = 28 days

Footnotes on following page:

1. For women of childbearing potential only. Must be done ≤ 7 days prior to registration. If the urine test is positive or cannot be confirmed as negative, a serum pregnancy test will be required
2. Affected immunoglobulin refers to the baseline M-protein type, that is, IgG, IgA, or IgD. Not applicable if patient “non-secretory” or if patient has no heavy chain, i.e. light chain myeloma. Affected immunoglobulin is required after baseline only if it used for disease monitoring instead of SPEP (e.g. IgA myeloma).
3. Baseline then only if clinically indicated.
4. Optional BM sample submission for patients who discontinue treatment due to disease progression or relapse, intolerable AEs, patient refusal, subsequent treatment for myeloma.
5. Urine Electrophoresis required only if used to assess disease response
6. Bone marrow aspirate done at the end of Cycle 1 (prior to cycle 2) will be paid for by research.
7. Immunofixation (IF) only needed in absence of M-Spike to document CR or SCR

R Collected as part of the IRB# 521-93, IRB# 14-009163 and/or IRB# 919-04

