11.2 Confirmed response

In order to be classified as a hematologic response, confirmation of serum M- protein, serum immunoglobulin free light chain (when primary determinant of response) and urine M- protein (when primary determinant of response) results must be made by verification on two consecutive determinations.

- Bone marrow aspirate and biopsy are **only** required to document CR or sCR, except for patients with evaluable disease **only**, where a bone marrow is required to document all response categories including progression. However, a second confirmatory bone marrow is **not** required to confirm response in any case.
- Radiographic studies are not required to satisfy these response requirements; however, if radiographic studies were performed there should be no evidence of progressive or new bone lesions.

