11.4 Response and Progression

Criteria for response and progression are listed in Table 11.5. Progressive disease for all patients as defined in Table 11.5.

Table 11.5

STANDARD IMWG RESPONSE CATEGORY	RESPONSE CRITERIA ^a
Stringent Complete Response (sCR) ^b	
CR as defined plus
 
Normal FLC ratio and
 
 • Absence of clonal PCs by immunohistochemistry or 2- to 4- color flow cytometryⁱ
Complete Response (CR) ^b	
 • Negative immunofixation of serum and urine^c and • Disappearance of any soft tissue plasmacytoma and • <5% PCs in Bone Marrow and • If the only measurable disease is FLC, a normal FLC ratio^d • For patients with extramedullary plasmacytoma present at baseline: a) FDG-avid or PET positive prior to therapy: Mass of any size permitted if PET negative and b) Variably FDG-avid or PET negative: Regression to normal size on CT. For patients with only skin involvement, these same criteria apply to skin lesions measured with a ruler.
Very Good Partial Response (VGPR)	
 • Serum and urine M-protein detectable by immunofixation but not on electrophoresis^c or • ≥90% reduction in serum M-protein and urine M-protein <100 mg/24 h^c • If the only measurable disease is FLC, a >90% reduction in the difference between involved and uninvolved FLC levels • Not applicable for those patients who do not have a “measurable” serum M-spike, serum free light chain, or urine M-spike at baseline
Partial Response (PR)	
 • If present at baseline, ≥ 50% reduction of serum M-protein and reduction in 24-hour urinary M-protein by ≥90% or to <200 mg/24hrs^c • If the only measurable disease is FLC, a ≥50% reduction in the difference between involved and uninvolved FLC levels • If the only measurable disease is BM, a ≥ 50% reduction in BM PCs (provided the baseline PCs was ≥ 30%)

	
 • If present at baseline, $\geq 50\%$ reduction in the size (SPD) of soft tissue plasmacytomas ^j • For patients with extramedullary plasmacytoma present at baseline: $\geq 50\%$ decrease in SPD of up to 6 largest dominant masses and a) FDG-avid or PET positive prior to therapy: one or more PET positive at previously involved sites OR b) Variably FDG-avid or PET negative: regression on CT or by measurements with a ruler in patients with only skin involvement

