12.0 Descriptive Factors

- 12.1 Prior treatment: 0 vs 1 vs 2 vs 3+
- 12.2 Parameters followed for hematologic response: serum monoclonal protein ≥ 0.5 g/dL and urine monoclonal protein ≥ 200 mg/24 hours vs. serum monoclonal protein ≥ 0.5 g/dL only vs. urine monoclonal protein ≥ 200 mg/24 hours only vs. serum immunoglobulin free light chain ≥ 10 mg/dL vs. bone marrow plasma cells $\geq 30\%$ vs. measurable bone or extramedullary disease on imaging. Distinguish between SPEP measurements versus quantitative IgA measurements versus quantitative IgD measurements for serum monoclonal protein.
- 12.3 mSMART FISH risk level: high risk vs low risk vs unknown.

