16.2 Statistical Design

Due to the lack of data to identify relevant biomarkers, the estimation of RR would be of interest. In each group, the response rates will be examined to see if there's any preliminary evidence to suggest further studies. This study will not utilize a formal statistical design.

For each biomarker category, the RR will be estimated by the number of patients who achieve a PR or better divided by the total number of evaluable patients in each cohort. Exact binomial 95% confidence intervals for these rates will be calculated.

16.22 Sample Size: A maximum of 30 evaluable patients will be accrued in cohort A and B and 60 patients in cohort C and D respectively. We anticipate accruing an additional 2 in cohort A and B and 3 in cohort C and D to account for ineligibility, cancellation, major treatment violation, or other reasons. Therefore, the maximum projected accrual is 190 patients (A: 32, B: 32, C: 63 and D: 63).

16.23 Accrual Rate and Study Duration: The anticipated accrual rate is 6 evaluable patients per month. Therefore, the accrual period for this pilot study is expected to be approximately 32 months. The final analysis can begin approximately 35 months after the trial begins, i.e. as soon as the last patient has been observed for 1 months and allowing 2 months for data entry.

16.24 Other considerations: Adverse events, quality/duration of response, and patterns of treatment failure observed in this study, as well as scientific discoveries or changes in standard care will be taken into account in any decision to terminate the study

16.3 Analysis Plan.

The analysis for this study is planned to start after data maturity has occurred. It is anticipated that the earliest date in which the result will be available via manuscript, abstract or presentation after the last registered patient has been followed for at least 1 month.

16.31 Primary Outcome Analyses:

Each cohort (A-D) will be evaluated separately and independently.

16.311 Definition:

The primary endpoint of this study is RR after 1 cycle of treatment. RR is defined as a binary variable. A success will be defined as patient who achieve a response of a PR or better using the IMWG criteria (Section 11.0) after one cycle of treatment. All patients meeting eligibility criteria who have signed a consent form, who complete at least one cycle of treatment and have successfully submitted biospecimens (pre and post treatment) will be evaluable for the endpoint.

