Estimation: For each biomarker of interest, RR will be calculated by the number of successes divided by the total number of evaluable patients in each cohort.

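### Patients with imaging-only disease count in the primary denominator, but the plan neither requires that disease to be re-measured after cycle 1 nor gives a partial-response rule for bone lesions

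*Combined protocol and SAP*

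**What the plan says.** All references are to the combined protocol and SAP.

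- **Entry.** Inclusion criterion 3.13 is "Measurable disease as defined in section 11.0". The list in 11.1 ends with "Measurable bone or extramedullary disease on imaging". Section 12.2 confirms that this is a foreseen category: among the parameters followed for response it names "measurable bone or extramedullary disease on imaging" as a level of its own, apart from M-protein, free light chain (FLC) and marrow.
- **Denominator.** Under 16.311, eligible, consented patients "who complete at least one cycle of treatment and have successfully submitted biospecimens (pre and post treatment) will be evaluable for the endpoint". The estimation paragraph adds that "RR will be calculated by the number of successes divided by the total number of evaluable patients in each cohort".
- **Schedule.** The test schedule in 4.0 marks the WBLDCT or PET/CT row before cycle 2 and before cycles 3 to 6, but footnote 3 qualifies both entries: "Baseline then only if clinically indicated".
- **Response rules.** Section 11.2 states "Radiographic studies are not required to satisfy these response requirements". Footnote a of Table 11.5 repeats this. Neither makes an exception for patients whose only disease is on imaging.
- **Partial response.** For soft-tissue disease, Table 11.5 asks for at least a 50% "reduction in the size (SPD) of soft tissue plasmacytomas", with a parallel size rule for extramedullary plasmacytoma. It has no partial-response row for bone lesions. The marrow row applies only when marrow is the sole measurable disease and baseline plasma cells were at least 30%.
- **Marrow rule.** Section 11.2 also says that patients with evaluable disease only (in 11.1, no measurable serum M-protein, FLC or urine M-protein) need a marrow to document every response category.

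**The concern.** The primary endpoint is response after one cycle. A patient in its denominator should have the followed disease measured again at that time, under a criterion that can return either answer. For imaging-only patients the plan guarantees neither. Their label could then be set by the absence of a measurement instead of by the drug's effect.

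Two things are at stake. The cohort response rate can be biased by patients who were not truly assessed. The same labels also feed the biomarker logistic regressions in 16.321 and the depth-of-response analysis in 16.323, where a mislabelled patient weakens or distorts an association. In a biomarker category smaller than the cohort, each such patient weighs more.

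**Working it through.** **1. Cohort sizes.** Section 16.22 gives 30, 30, 60 and 60 evaluable patients plus allowances of 2, 2, 3 and 3: (30+2) + (30+2) + (60+3) + (60+3) = 190. This matches the plan's stated maximum. The denominators used below are 30 and 60.

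**2. Routes to success for an imaging-only patient under Table 11.5.**

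| Route | Open to an imaging-only patient? |
|---|---|
| Partial response by M-protein or FLC | No; neither is measurable at baseline |
| Partial response by marrow | No; marrow is not the sole measurable disease |
| Partial response by lesion size | Only if lesions are soft-tissue or extramedullary and are measured again |
| Partial response for bone lesions | No criterion exists, scanned or not |
| Very good partial response | Excluded without a measurable serum M-spike, FLC or urine M-spike |
| Complete response | Needs negative immunofixation and under 5% marrow plasma cells; a bone-only patient has no plasmacytoma condition to meet, so no scan is needed |

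A patient who meets none of these and has not progressed falls into stable disease, the residual category, which is not a success.

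**3. Does the pre-cycle-2 marrow close the gap?** No. Section 11.2 sends these patients to marrow for every category, but Table 11.5 has no marrow partial-response rule for them. In 4.0, the marrow before cycle 2 is a research sample. The clinical aspirate-and-biopsy row is marked at baseline only, and the plasma cell assessment row has no entry after cycle 1. Section 14 describes the sample's use in metabolomics, genomics and transcriptomics and does not call for a plasma-cell percentage.

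**4. Size.** Let p be the true one-cycle response rate, n the evaluable patients and k the imaging-only patients scored as non-responders. The expected rate is p × (n − k)/n, so the loss is p × k/n. The documents give neither k nor p; I assume k = 1, 3 or 6 and p = 40% to 80%.

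| n | k | Loss at p = 40% | Loss at p = 60% | Loss at p = 80% |
|---|---|---|---|---|
| 30 | 1 | 1.3 points | 2.0 | 2.7 |
| 30 | 3 | 4.0 | 6.0 | 8.0 |
| 30 | 6 | 8.0 | 12.0 | 16.0 |
| 60 | 1 | 0.7 | 1.0 | 1.3 |
| 60 | 3 | 2.0 | 3.0 | 4.0 |
| 60 | 6 | 4.0 | 6.0 | 8.0 |

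For example, with p = 80%, n = 30 and k = 1: 0.80 × 1/30 = 2.7 points.

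**5. Against the exact 95% intervals**, with p = 60% and k = 3:

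- n = 30: 0.6 × 27 = 16.2, taken as 16 responders. Included, 16/30 = 53.3% (34.3 to 71.7); excluded, 16/27 = 59.3% (38.8 to 77.6).
- n = 60: 0.6 × 57 = 34.2, taken as 34 responders. Included, 34/60 = 56.7% (43.2 to 69.4); excluded, 34/57 = 59.6% (45.8 to 72.4).

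**The case against.** A reader might infer that these patients are never scanned and are automatically counted as failures, so that the rate is always biased downward in all four cohorts. The documents do not support that reading.

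- A scan before cycle 2 is listed, conditional on clinical indication. Section 12.2 treats imaging as a followed parameter, and 18.5 names PET and skeletal survey among possible supporting documents for response. Sites may well scan such patients. What stands is that nothing requires it.
- No rule says how an unassessed cycle-1 response is counted. Scoring it as non-response is an inference from the residual stable-disease category.
- The error can run upward, through the literal complete-response wording for a bone-only patient.
- Skin-only lesions are measured by ruler, so they need no scan.
- Cohort A should be little affected. Criterion 3.12 excludes more than one focal MRI lesion and requires at least 10% clonal marrow plasma cells.

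It is also fair to say that this is an estimation pilot without a formal design, and that the shifts in step 5 lie well inside the intervals. That limits the severity. It does not remove the point: the shift is systematic and the interval does not account for it. The conflict between 11.2 and Table 11.5 remains whatever the number of patients.

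**Conclusion.** The point holds as a gap between eligibility, denominator, schedule and response criteria. Imaging-only patients are eligible and evaluable, no scan is mandatory at the primary time point, and Table 11.5 gives them a partial response only by lesion size, with none for bone. Their cycle-1 response may therefore not reflect the disease being followed. Most would land in stable disease and lower the rate; a few could be scored as responders without a scan.

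The per-patient loss of 1.3 to 2.7 points at n=30 and 0.7 to 1.3 points at n=60 rests on an assumed response rate of 40% to 80% and on every such patient being scored a non-responder. The total effect depends on their number, which the documents do not give. It is probably modest, but it falls on the primary endpoint and is cheap to remove, so the text should be changed.

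**What to change.** 1. **In 16.311, add a baseline condition to evaluability.** Count a patient for the primary endpoint only if at least one of serum M-protein, urine M-protein or involved FLC was measurable at baseline and is the marker followed. The schedule already repeats these before cycle 2 (urine where it is used to assess response). Include marrow-only patients (at least 30% plasma cells) only if a plasma-cell percentage is recorded from the aspirate already taken before cycle 2. Because the condition is set at baseline, for the M-protein and FLC routes it does not select on outcome.
2. **Report imaging-only patients separately**, by cohort, with a sensitivity analysis that returns them to the denominator as non-responders. State how an unassessed cycle-1 response is counted.
3. **Reconcile footnote 3 of 4.0, section 11.2, and Table 11.5 with its footnote a** for this group, including the missing bone criterion and the marrow rule that has no matching partial-response row.

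This takes a few sentences and no additional scan. The cost is that a few patients no longer count toward the cohort totals. They would draw on the allowances in 16.22 (2 each in A and B, 3 each in C and D), which also cover ineligibility, cancellation and major violations, so those allowances should be checked against the expected number of imaging-only patients.
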